8.5.3 Safety Monitoring for Platelet Count Results

All patients will have platelet counts monitored every 14 days (± 2 days) for the duration of the study treatment period and must not receive Study Drug without an interpretable platelet count result in the prior 14 days. Upon completion of the study treatment period, platelets will be monitored every 14 days (± 2 days) for the first 6 weeks and then at 8 and 13 weeks post end of treatment period (as per visit schedule).

As described in [Section 6.2.1](#), all platelet count results must be reviewed promptly (within 48 hours of receipt) by the Investigator or the designee to ensure that the count has not met the stopping rule and to determine whether the rate of decline is suggestive that the patient could be approaching the dose interruption rule of 75,000/mm³ as specified in [Section 8.6.3](#).

Any case of a platelet count reduction to levels below 50,000/mm³ (Grade 3 or Grade 4) is considered an adverse event of special interest and should be reported in an expedited fashion to the Sponsor. In this case the Investigator should refer the subject to a hematologist to provide diagnostic and therapeutic management.

Lab alerts related to platelet monitoring/stopping rules are issued when: 1) platelet counts are < 140,000 mm³, 2) platelet count is $\geq 30\%$ decreased from Baseline, or 3) the hematology sample is unreportable. All these lab alerts, are reviewed promptly by the Medical Monitor and instructions are communicated to the Investigator and the study personnel within 24 hours of receiving an actionable lab alert as described in [Section 6.2.1](#).

Actions to be taken in the event of reduced platelet count are shown in [Table 3](#) in [Section 8.6.3](#).

In the event of a platelet count < 100,000/mm³ the laboratory tests outlined in [Appendix E](#), should be performed as soon as possible. Additional lab tests will be determined by the Sponsor Medical Monitor or designee in consultation with the Investigator.

8.5.4 Safety Monitoring for Bleeding Events

Patients will be evaluated for occurrence of bleeding events continuously after the start of Study Drug treatment (Day 1) up to the end of the follow-up period for all cohorts. All bleeding events are considered adverse events and reported on adverse event case report form.

Bleeding events that are either major or clinically-relevant non-major bleeding (as defined below) will need to be monitored and treated, as needed, immediately. Patients with a suspected bleeding event will undergo additional testing if deemed appropriate by the treating physician and an (S)AE case report form will be completed. In addition, if bleeding is considered significant, hemoglobin (Hb), hematocrit (HCT), aPTT, PT, INR, and platelet count are to be obtained. In addition, approximately 2 mL of K2EDTA anticoagulated blood will be collected and resulting plasma must be stored allowing for a centralized assessment of ISIS 678354 concentrations.

If a minor bleeding event occurs, the Investigator should notify the Sponsor Medical Monitor (or designee) and additional testing of coagulation parameters (aPTT, prothrombin time [PT], INR), platelet count, and platelet volume may be performed.

Major bleeding (MB) is defined as one of the following ([Büller et al. 2007](#)):

1. Fatal bleeding
2. Symptomatic bleeding in a critical area or organ, such as intracranial, intraspinal, intraocular, retroperitoneal, intraarticular if in a major joint, or pericardial, or intramuscular with compartment syndrome

3. Clinically overt bleeding leading to transfusion of ≥ 2 units of packed red blood cells or whole blood or a fall in hemoglobin of 20 g/L (1.24 mmol/L) or more within 24 hours

Clinically-relevant non-major bleeding is defined as overt bleeding not meeting the criteria for major bleeding but that resulted, for example, in medical examination, intervention, or had clinical consequences for a subject (Büller et al. 2007).

Minor bleeding events are those that do not fulfill the criteria for major bleeding or clinically-relevant, non-major bleeding events (defined above), for example excess bruising, petechiae, gingival bleeding on brushing teeth.

8.5.5 Safety Monitoring for Constitutional Symptoms

Patients will be instructed to promptly report any signs or symptoms of fever, constitutional symptoms, rash, arthralgia or joint swelling that may arise during the study and the Investigator should closely evaluate all potential causes, including concomitant illness. Patients who experience persistent or increasing symptoms should be discussed with the Sponsor Medical Monitor or designee to determine whether additional monitoring or laboratory tests are required.

8.5.6 Safety Monitoring for Insulin, Oral Antidiabetic Medication and Glucose

All patients on insulin will monitor their glucose levels with a glucometer as per standard practice guidelines and bring their glucometer or glucometer log printout to every clinic visit. In addition, patients who are not on insulin but use a glucometer should also bring their glucometer and/or glucometer log printout to every clinic visit.

- The Investigator or delegate will review the glucometer reading or printout at every clinic visit to evaluate if fasting pre-breakfast self-monitored plasma glucose values exceed threshold values as per the Safety Monitoring Rules for Hyperglycemia below
All diabetic patients will note any changes in their insulin dose and /or oral antidiabetic therapy, as well as any hypoglycemic episode they may experience.
- The Investigator or delegate will ask patients at every clinic visit if they made changes in their insulin dose or oral antidiabetic therapy, and if they experienced a hypoglycemic episode
 - Patients will be instructed on the monitoring and management of hypoglycemic episodes at each visit
 - Documented symptomatic hypoglycemic episodes should be captured as adverse events in the respective CRF. Documented symptomatic hypoglycemia is defined as typical hypoglycemia symptoms accompanied by measured plasma glucose ≤ 70 mg/dL (≤ 3.9 mmol/L)
 - Any changes in insulin dose or oral antidiabetic therapy should be captured into the Concomitant Medication CRF

8.5.7 Safety Monitoring for Documented Severe Hypoglycemia

A documented severe hypoglycemic event is defined as one in which the patient requires assistance of another person to obtain treatment for the event and has a plasma glucose level

≤ 70 mg/dL (≤ 3.9 mmol/L). The rescue treatment of hypoglycemia may include IV glucose or buccal or intramuscular glucagon.

The definition of severe symptomatic hypoglycemia includes all episodes in which neurological impairment was severe enough to prevent self-treatment and which were thus thought to place patients at risk for injury to themselves or others. Note that “requires assistance” means that the patient could not help himself or herself. Someone being kind that assists spontaneously the patient when not necessary does not qualify as “requires assistance.”

Severe hypoglycemia will be qualified as a SAE only if it fulfills SAE criteria.

If a patient presents with symptoms of hypoglycemia, the Investigator will need to take immediate action to confirm the patient’s glucose level and treat the patient accordingly.

The experience of hypoglycemia may vary greatly from patient to patient. However, there are certain classical signs and symptoms, of which patients should be aware as a clue that their blood glucose may be low. Common symptoms include headache, heart pounding, confusion, disorientation, numbness or tingling, pale skin, shakiness or tremulousness, increased appetite, anxiousness or nervousness, lightheadedness or dizziness, sweating, and weakness. Coma could occur if blood sugar correction is not performed.

If patients suspect they might be having a hypoglycemia reaction, they should check their blood glucose using their meters as soon as possible, before treatment if possible, provided they feel it is safe to do so. If there is doubt about safety they should treat the event first, using some sugar, milk, or juice for example, then obtain and record a blood glucose value as soon as possible thereafter. The time and nature of treatment should be noted, and especially if any blood glucose result was before or after treatment. It would be helpful for the patient to note if a contributory factor (e.g., missed or reduced meals, unaccustomed physical activity) occurred earlier in the day of the event.

Instructions should be provided to all patients on the appropriate use of a glucose meter.

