Appendix D Grading Scale for Adverse Events Relating to Laboratory Abnormalities

Continued

Adverse Event	Mild	Moderate	Severe
Cardiac troponin T increased	Levels above the upper limit of normal and below the level of myocardial infarction as defined by the manufacturer	-	Levels consistent with myocardial infarction as defined by the manufacturer
CD4 lymphocytes decreased	<LLN - 500/mm ³ ; <LLN - 0.5 x 10 ⁹ /L	<500 - 200/mm ³ ; <0.5 - 0.2 x 10 ⁹ /L	<200/mm ³ ; <0.2 x 10 ⁹ /L
CPK increased*	>ULN - <6 ULN	6 - 10 x ULN	>10 x ULN
Creatinine increased	>1 - 1.5 x baseline; >ULN - 1.5 x ULN	>1.5 - 3.0 x baseline; >1.5 - 3.0 x ULN	>3.0 x baseline; >3.0 x ULN
GGT increased	>ULN - 2.5 x ULN	>2.5 - 5.0 x ULN	>5.0 x ULN
Hypercalcemia	Corrected serum calcium of >ULN - 11.5 mg/dL; >ULN - 2.9 mmol/L; Ionized calcium >ULN - 1.5 mmol/L	Corrected serum calcium of >11.5 - 12.5 mg/dL; >2.9 - 3.1 mmol/L; Ionized calcium >1.5 - 1.6 mmol/L; symptomatic	Corrected serum calcium of >12.5 mg/dL; >3.1 mmol/L; Ionized calcium >1.6 mmol/L; hospitalization indicated
Hyperglycemia	Fasting glucose value >ULN - 160 mg/dL; Fasting glucose value >ULN - 8.9 mmol/L	Fasting glucose value >160 - 250 mg/dL; Fasting glucose value >8.9 - 13.9 mmol/L	>250 mg/dL; >13.9 mmol/L; hospitalization indicated
Hyperkalemia	>ULN - 5.5 mmol/L	>5.5 - 6.0 mmol/L	>6.0; hospitalization indicated
Hypermagnesemia	>ULN - 3.0 mg/dL; >ULN - 1.23 mmol/L	-	>3.0 mg/dL; >1.23 mmol/L
Hypernatremia	>ULN - 150 mmol/L	>150 - 155 mmol/L	>155 mmol/L; hospitalization indicated
Hyperuricemia	>ULN - 10 mg/dL (0.59 mmol/L) without physiologic consequences	-	>ULN - 10 mg/dL (0.59 mmol/L) with physiologic consequences
Hypoalbuminemia	<LLN - 3 g/dL; <LLN - 30 g/L	<3 - 2 g/dL; <30 - 20 g/L	<2 g/dL; <20 g/L
Hypocalcemia	Corrected serum calcium of <LLN - 8.0 mg/dL; <LLN - 2.0 mmol/L; Ionized calcium <LLN - 1.0 mmol/L	Corrected serum calcium of <8.0 - 7.0 mg/dL; <2.0 - 1.75 mmol/L; Ionized calcium <1.0 - 0.9 mmol/L; symptomatic	Corrected serum calcium of <7.0 mg/dL; <1.75 mmol/L; Ionized calcium <0.9 mmol/L; hospitalization indicated
Hypoglycemia	<LLN - 55 mg/dL; <LLN - 3.0 mmol/L	<55 mg/dL; <3.0 mmol/L	<40 mg/dL (<2.2 mmol/L) AND requires assistance of another person to actively administer carbohydrates, glucagon, or take other corrective actions [‡]
Hypokalemia	<LLN - 3.0 mmol/L	<LLN - 3.0 mmol/L; symptomatic; intervention indicated	<3.0 mmol/L; hospitalization indicated

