If the imputed start date is later than the imputed end date, then set the imputed start date to the imputed end date.

Analysis period will be assigned by comparing the imputed medication start/end date with the period start/end date.

3.7.2 *Adverse Events*

All AEs will be coded by the Medical Dictionary for Regulatory Activities (MedDRA) version 20.1. Missing or partial dates will be imputed as outlined in Section 3.7.1.

Treatment-emergent adverse events (TEAEs) are defined as adverse events that occurred after the first dose of Study Drug. If the imputed onset date/time is the same as or after the date/time of the first dose of Study Drug, then the event is treatment emergent. An AE with a completely missing start date will be assumed to be treatment emergent.

In the situation where change in severity (but no change in seriousness) occurs for an AE, study sites are instructed to enter an end date for the original AE and start a new record for the AE with a new severity reported. In the new record, the changed severity is to be recorded and the start date will be set to be the end date of the previous record.

When counting the total number of treatment-emergent events for table display, events reporting an increase in severity will be counted as separate events.

AE summary tables by treatment group and overall will be presented in 2 periods separately: on-treatment and on-study. The frequency of patients with any incidence of AEs and the number of events will be summarized by SOC and PT for:

- TEAEs
- TEAEs related to Study Drug. Related is defined as “Related”, “Possible”, or missing relationship to Study Drug
- TEAEs by severity. At each level of patient summarization, a patient with multiple events is counted only once according to the worst reported severity. Adverse events with missing severity will be categorized as “Missing” for this summary.
- TEAEs related to Study Drug by severity
- Most common TEAEs. Most Common TEAE is defined as treatment-emergent adverse events with an incidence of 10% or more within any treatment groups at PT level.
- Treatment Emergent SAEs
- Treatment Emergent SAEs related to Study Drug
- TEAEs leading to permanent treatment discontinuation
- TEAEs leading to death.

Summary tables will be sorted by decreasing frequency of SOC and then by decreasing frequency of PT within SOC in pooled ISIS 678354 group. If the frequency is the same for multiple PTs, sort alphabetically.

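### An assisted hypoglycaemic event at 40 to 70 mg/dL is severe by protocol 8.5.7 but cannot be graded Severe under Appendix D, so the severity tables can understate it

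*Combined protocol and SAP*

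**What the plan says.** Protocol 8.5.7 defines a documented severe hypoglycaemic event as one in which the patient "requires assistance of another person to obtain treatment for the event and has a plasma glucose level" of at most 70 mg/dL (3.9 mmol/L). The next paragraph describes severe symptomatic hypoglycaemia as every episode in which the patient was too neurologically impaired to treat himself or herself, and attaches no glucose value. On seriousness it says: "Severe hypoglycemia will be qualified as a SAE only if it fulfills SAE criteria".

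Protocol 9.4.3.2 bases the severity grade of adverse events on CTCAE version 4.03 and points to Appendix D. The general mild/moderate/severe wording in that section is kept for events that Appendix D does not list. Hypoglycaemia is listed:

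- Severe: "<40 mg/dL (<2.2 mmol/L) AND requires assistance of another person to actively administer carbohydrates, glucagon, or take other corrective actions"
- Moderate: "<55 mg/dL; <3.0 mmol/L"
- Mild: "<LLN - 55 mg/dL; <LLN - 3.0 mmol/L"

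Protocol 8.5.6 has documented symptomatic episodes at 70 mg/dL or below recorded as adverse events. SAP 3.7.2 tabulates treatment-emergent events, and those related to Study Drug, by severity, where "a patient with multiple events is counted only once according to the worst reported severity". The SAP's section on events of special interest (3.7.2.3) covers bleeding only. No SAP table counts events that meet the 8.5.7 definition.

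**The concern.** The two passages use the same word and the same criterion, the need for another person's help, but with different glucose limits. An investigator who follows 9.4.3.2 must record as Moderate or Mild an event that 8.5.7 calls severe. An investigator who takes the grade from the 8.5.7 definition will record severe.

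The events are plausible in this population. Inclusion criterion 3b requires treated type 2 diabetes, 8.5.6 provides for patients on insulin, and insulin use is a planned subgroup in SAP 3.3.4. Safety is part of the primary objective. At stake is whether a reader of the severity tables would see that a patient needed rescue by someone else.

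**Working it through.** The plan states no figure on this point, so there is none to reproduce. The check applies both definitions as decision rules to an assisted event.

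**Inputs.** The 8.5.7 limit of 70 mg/dL or below; the Appendix D limits of below 40 with assistance (Severe), below 55 (Moderate), and below LLN down to 55 (Mild). The glucose LLN is not in the documents, so 60, 65 and 70 mg/dL are assumed in turn.

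**Units.** At 18.016 mg/dL per mmol/L, 40, 55 and 70 mg/dL are 2.22, 3.05 and 3.89 mmol/L, against printed values of 2.2, 3.0 and 3.9. Each pair agrees to within 1 mg/dL, so the conflict is not a conversion slip.

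**Both rules, assisted event:**

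| Glucose (mg/dL) | 8.5.7 | Appendix D |
|---|---|---|
| below 40 | severe | Severe |
| 40 to below 55 | severe | Moderate |
| 55 to below LLN | severe | Mild |
| LLN to 70 | severe | no grade |
| above 70 | not severe | no grade (if LLN is 70 or lower) |

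The edges matter. Exactly 40 is Moderate, because Severe needs a value below 40. Exactly 55 is Mild, because Moderate needs a value below 55. Exactly 70 is severe under 8.5.7, because that limit is inclusive.

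**Count over the 31 whole values from 40 to 70 mg/dL.** Section 8.5.7 gives severe at all 31 and Appendix D gives Severe at none:

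| Assumed LLN | Moderate | Mild | No grade |
|---|---|---|---|
| 60 | 15 | 5 | 11 |
| 65 | 15 | 10 | 6 |
| 70 | 15 | 15 | 1 |

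These are counts of glucose values, not expected numbers of patients. If the LLN were above 70, the ungraded band would vanish and the split would be 15/16/0. Only the Moderate band (40 to 54) is independent of the LLN.

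**Where an ungraded event goes.** Hypoglycaemia is listed in Appendix D, so 9.4.3.2 does not clearly allow the general scale for a value from LLN to 70. SAP 3.7.2 puts events without a severity into a Missing category.

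**Effect on a table row.** Each active group has 25 × 4/5 = 20 planned patients, and pooled placebo has 4 × 25 × 1/5 = 20. One patient regraded out of severe moves the hypoglycaemia row by 1/20 = 5 percentage points. A row for the whole system organ class moves only if that patient has no other severe event in the class.

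**The case against.** The strongest reply is that the protocol already names the governing scale. Section 9.4.3.2 sends listed events to Appendix D. Section 8.5.7 sits among the safety monitoring rules and never says that it fills the severity field, so one event can carry both labels. The Severe cell in Appendix D also has a footnote saying that it was modified to agree with diabetes and endocrine society guidelines, so it looks like a considered edit. This stands in part: sites have a rule, and inconsistent grading is a risk rather than a certainty. It does not remove the problem. Following the rule is what produces the understatement, and the Appendix D cell contains the assistance criterion itself, so both texts address the same event. Appendix D also calls its rows recommendations, which leaves room for an investigator to record severe.

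The second reply is that little depends on the 8.5.7 class, and this stands. It is not a safety endpoint (protocol 10.1.3, SAP 1.4.4), not an event of special interest (protocol 9.3.3.1), and not a stopping rule (protocol 8.6). Seriousness is judged separately, and the event still counts in overall incidence and appears in the listings. A reader might infer that serious events would be missed or that the arms would be biased against each other. The documents support neither: the SAE criteria apply whatever the grade, and the same grading rules apply to every arm.

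A reader might also say flatly that an assisted event at 60 mg/dL is Mild. That needs an LLN above 60, which the documents do not give. At 50 mg/dL the Moderate grade follows without any assumption.

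There may be a partial safeguard. SAP 3.7.4 plans a listing of patients who met safety monitoring rules, and SAP 2.4.1 counts glycaemic control among those rules. The SAP does not say whether 8.5.7 events will appear there. If they do, that listing and the severity table will describe the same event differently.

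**Conclusion.** The point holds as an internal contradiction of minor weight. For every assisted event from 40 to 70 mg/dL, 8.5.7 says severe and Appendix D does not. Below 40 mg/dL with assistance they agree. The consequence is confined to the tables by severity, which can understate these events, and to possible inconsistency in how sites grade them. The documents give no hypoglycaemia rate, so the number affected cannot be estimated and may be zero. The figure of 5 percentage points per patient assumes the planned group size of 20. The split between Mild and no grade rests on assumed LLN values; that none of these events reaches Severe does not.

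**What to change.** Reconcile protocol 8.5.7, 9.4.3.2 and Appendix D so that one definition determines the severity grade of an assisted hypoglycaemic event, and so that every glucose value within that definition receives a grade. Which threshold to use is for the sponsor's clinical team.

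In the SAP, add a count or listing by treatment group of events meeting the 8.5.7 definition, separate from the severity grade, with the glucose value where recorded. This also covers events that sites have already graded, which a clarification alone would not change. The listing should show whether the glucose was measured before or after treatment where that is known, because 8.5.7 lets patients treat first and measure later.

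A table by glucose band is optional. It depends on the eCRF holding event-level glucose and an assistance indicator as usable fields, which the documents do not show.

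The cost is one protocol clarification and one short listing or count. No endpoint, analysis model or sample size changes.

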8.5.8 Safety Monitoring for Hyperglycemia in Patients with T2DM

If medically appropriate, patients should remain on a stable regimen of anti-hyperglycemic therapy and have either upward dose titration and/or addition of any other anti-hyperglycemic agent(s) only when specific threshold values (listed below) are met and confirmed on subsequent testing (ideally within 1-week of the initial test). Any change to the anti-hyperglycemic therapy should be discussed with the Sponsor Medical Monitor prior to introduction.

Fasting plasma glucose (FPG) and HbA1c are monitored as per visit schedule in [Appendix A](#) (approximately every 3 months) throughout the study. In addition, patients on insulin should self-monitor their plasma glucose (SMPG) routinely on a glucometer. If a fasting pre-breakfast SMPG value exceeds the specific glycemic limit, the patient should check it again on the following 2 days. If all the fasting pre-breakfast values on 3 consecutive days exceed the specific limit, the patient should contact the Investigator and an unscheduled central laboratory FPG measurement and HbA1c should be performed.

The threshold values are defined as:

- FPG > 270 mg/dL (15.0 mmol/L) or
- HbA1c > 9% (for patients with baseline HbA1c < 8%) and HbA1c increase of more than 1% from Baseline (for patients with baseline HbA1c \geq 8 and < 9%)

In case of confirmed FPG/HbA1c above the threshold value, the Investigator should ensure that no reasonable explanation exists for insufficient glucose control and in particular that:

- Plasma glucose was actually measured in the fasting condition (i.e., after at least 10 hours fast)
- Absence of intercurrent disease which may jeopardize glycemic control. In case of an emergency (e.g., surgery, infection), the Investigator can take appropriate measures for glycemic control
- Compliance to treatment is appropriate
- Compliance to diet and lifestyle is appropriate

If any of the above can reasonably explain the insufficient glycemic control, the Investigator should consider the following:

- Investigation and treatment of intercurrent disease (to be reported in adverse event (AE)/concomitant medication parts of the e-CRF)
- Stress on the absolute need to be compliant to treatment
- Organize a specific interview with a Registered Dietician or other qualified nutrition professional and stress on the absolute need to be compliant to diet and lifestyle recommendations

A FPG/HbA1c follow-up assessment should be arranged after appropriate action has been taken.

